## 7. CHANGES FROM PROTOCOL

- **Changes for the primary analysis:**

The mITT population is defined in [Section 5.2.2](#) and is used for the analysis of primary and secondary efficacy endpoints. In addition, sensitivity analyses will be conducted for the primary and secondary efficacy endpoints in the ITT population.

- **Rationale for the changes:**

- Recently published observational data suggest that patients with PUL 2.0 entry score 1 have minimal PUL 2.0 changes over a one-year treatment period [19]. Consequently, there is no meaningful opportunity to demonstrate the benefit of a therapeutic drug in the PUL 2.0 entry score 1 subpopulation. This information was published in April, 2023, after the study was already designed.
- This is the largest observational study of PUL 2.0 scores to date in 311 patients followed longitudinally over 24 months with 808 paired assessments [19]. In this study, the decline of PUL 2.0 scores for patients with a PUL 2.0 entry score of 1 was very low at 12 and 24 months compared to patients with higher PUL 2.0 entry scores. For example:
  - At 12 months, the mean PUL 2.0 total score change on all the paired assessments for patients with PUL 2.0 entry scores of 1 was -0.84 compared to -2.05 for PUL 2.0 entry score of 3. Changes were even greater for patients with PUL entry scores of 4, 5, or 6.
  - At 24 months, the mean PUL 2.0 total score change on all the paired assessment for patients with PUL 2.0 entry scores of 1 was -1.78 compared to -3.82 for patients with PUL 2.0 entry score of 3. Changes were even greater for patients with PUL 2.0 entry scores of 4, 5, or 6.
- Based on these results, the authors concluded that differences in PUL 2.0 entry scores should be taken into account when designing and analyzing clinical studies [19] and this supports the proposed change to the analysis population to exclude patients with a PUL baseline score of 1.
- Based on these results, the authors concluded that differences in PUL 2.0 entry scores should be taken into account when designing and analyzing clinical studies [19].
- In an early study by Pane from a cohort of 187 patients with DMD, which included 90 non-ambulatory patients, patients with the lowest PUL entry scores of 0 or 1 had minimal further progression during a 12-month follow-up period.
- Expert guidance from key opinion leaders for PUL 2.0 [REDACTED] strongly support the approach of removal of patients with PUL 2.0 entry scores of 1 because these patients do not demonstrate significant decline over a 1-year period and therefore impact meaningful opportunity to demonstrate efficacy.

- Based on changes in the external environment for DMD studies, the Sponsor conducted an analysis of current trials from clinicaltrials.gov and concluded that other clinical trials in the non-ambulatory DMD patient population using the PUL 2.0 as a primary endpoint measure have excluded patients with a PUL 2.0 entry score of 1 at baseline. For example, Capricor Inc./NCT05126758 A Phase 3, Randomized, Double-Blind, Placebo-Controlled Trial Evaluating the Efficacy and Safety of Human Allogeneic Cardiosphere-Derived Cells for the Treatment of Duchenne Muscular Dystrophy A Study of CAP-1002 in Ambulatory and Non-Ambulatory Patients with Duchenne Muscular Dystrophy (HOPE-3).
- Non-ambulatory DMD patients have limited treatment options and have been excluded from clinical trials in emerging treatment classes. Modification of the analysis will result in benefit to non-ambulatory patients as well as increased treatment options.
- The Sponsor has determined that removal of patients with a baseline PUL 2.0 entry score of 1.0 will result in approximately 15 patients removed from the ITT population. The sample size and power calculations are based on the assumptions described in the protocol, and with 15 fewer subjects out of 97 dosed subjects, the trial will have 87% power with 82 subjects in the mITT population.
- Sample size calculation was updated per the latest literature publications and study enrollment. The testing sequence of secondary endpoints was changed from the protocol.
- Changed the analysis method for subscores of regional dimensions (High-level (Shoulder), Distal-level (Wrist and Hand)) of PUL from MMRM to RCM, the same one used in the primary analysis.
- The analysis methods for change from baseline at week 52 in LVEF, Fibrosis Score of the Biceps Brachii, Cardiac Fibrosis Score, Myocardial Circumferential Strain [Global Circumferential Strain (GCS)%] percentage are changed from MMRM to ANCOVA respectively, because there are only two assessments performed during the study for these exploratory endpoints – one at baseline and the other at week 52 and it is not suitable for mixed models of repeated measures.
- MMRM ([Section 6.6.1.2.1](#)), Cumulative Loss of Function Analysis ([Section 6.6.1.2.8](#)) are added as sensitivity analyses for the primary efficacy endpoint.
- Added the composite of endpoints - mean observed z scores sequentially across 4 endpoints (PUL, ppFVC, Grip Strength, LVEF%) at week 52, namely, the mean z-scores for PUL + ppFVC, PUL + ppFVC + Grip Strength, PUL + ppFVC + Grip Strength + LVEF%, to the secondary endpoint. Analysis with the Composite of Endpoints ([Section 6.6.2.4](#)) is added as additional analysis for PUL.
- Change in the total score of Mid-level of PUL from baseline to Week 52 is added as a secondary endpoint.

**9. APPENDICES**

## APPENDIX 1. HANDLING MISSING/INCOMPLETE DATES

### A.1 Missing/Incomplete AE Onset Date

The following imputation rules apply to the case where the start date is incomplete (i.e., partially missing) for adverse events.

#### A.1.1 Missing start time

AEs with missing start times and which occur on a study-drug-dosing day will be considered as occurred after the study drug administration on that day, that is, it will be considered as TEAE. No imputation on other missing times.

#### A.1.2 Missing day and month

If the year is same as the year of first day on double-blind study medication, then the day and month of the start date of double-blind study medication will be assigned to the missing fields.

If the year is not the same as the year of first day on double-blind study medication, then January 1 will be assigned to the missing fields.

#### A.1.3 Missing month only

Treat day as missing and replace both month and day according to the above procedure.

#### A.1.4 Missing day only

If the month and year are same as the year and month of first day on double-blind study medication, then the start date of double-blind study medication will be assigned to the missing day.

If the month and year are not the same as the year and month of first day on double-blind study medication, then the first day of the month will be assigned to the missing day.

**Table 4: Analysis Date Derivation Rules for Missing/Incomplete AE Onset Date**

Reported Date	Date of First Drug Intake	Analysis Date (Derived)
--/MM/YYYY	DD/MM/YYYY	
--/02/2008	14/02/2008	14/02/2008*
--/02/2008	14/02/2007	01/02/2008
--/02/2008	14/02/2009	01/02/2008
--/--/YYYY	DD/MM/YYYY	
--/--/2008	14/02/2008	14/02/2008
--/--/2008	14/02/2007	01/01/2008
--/--/2008	14/02/2009	01/01/2008
DD/--/----		
--/MM/----		No imputation
--/--/----		

\*Death date has to be taken into consideration when calculating this.

If the stop date is complete and the imputed start date as above is after the stop date, the start date will be imputed by the stop date.

### A.2 Missing/Incomplete AE Stop Date

If needed, the following imputation rules apply to the case where the end date is incomplete (i.e., partially missing) for adverse events. Other partial end dates will not be imputed.

**A.2.1 Missing day and month, or Missing month only**

December 31 will be assigned to the missing fields.

**A.2.2 Missing day only**

The last day of the month will be assigned to the missing day.

**Table 5: Analysis Date Derivation Rules for Missing/Incomplete AE Stop Date**

Reported Date	Analysis Date (Derived) *
--/MM/YYYY	Set as last day of the month 31/MM/YYYY or
	30/MM/YYYY or
	29/MM/YYYY or
	28/MM/YYYY
--/--/YYYY	31/12/YYYY
DD/--/----	No imputation
--/MM/----	
--/--/----	

\*Death date has to be taken into consideration when deriving this.

**A.3 Missing/Incomplete Prior or Concomitant Medication Start Date**

For prior or concomitant medications, incomplete (i.e., partially missing) start date is imputed the same way as for the AE described above. When the start date and the stop date are both incomplete for a patient, impute the start date first.

The following rules will be applied to impute the missing start date. If the stop date is complete and the imputed start date is after the stop date, then the start date will be imputed using the stop date.

**A.3.1 Missing day and month**

If the year of the incomplete start date is the same as the year of the first dose date of double-blind study medication, then the day and month of the first dose date will be assigned to the missing fields.

If the year of the incomplete start date is not the same as the first dose date of double-blind study medication, then January 1 will be assigned to the missing fields.

**A.3.2 Missing month only**

Treat day as missing and replace both month and day according to the above procedure.

**A.3.3 Missing day only**

If the month and year of the incomplete start date are the same as the month and year of the first dose date of double-blind study medication, then the day of the first dose date will be assigned to the missing day.

If the month and year of the incomplete start date are the same as the first dose date of double-blind study medication, then the first day of the month will be assigned to the missing day.

#### **A.4 Missing/Incomplete Prior or Concomitant Medication Stop Date**

The following rules will be applied to impute the missing stop date, if needed. If the last dose date of double-blind study medication is missing, impute it with the last visit date. If the imputed stop date is before the start date (imputed or non-imputed start date), then the imputed stop date will be replaced with the start date.

##### **A.4.1 Missing day and month**

If the year of the incomplete stop date is the same as the year of the last dose date of double-blind study medication, then the day and month of the last dose date will be assigned to the missing fields.

If the year of the incomplete stop date is not the same as the year of the last dose date of double-blind study medication, then December 31 will be assigned to the missing fields.

##### **A.4.2 Missing month only**

Treat day as missing and replace both month and day according to the above procedure.

##### **A.4.3 Missing day only**

If the month and year of the incomplete stop date are the same as the month and year of the last dose date of double-blind study medication, then the day of the last dose date will be assigned to the missing day.

If the month and year of the incomplete stop date are not the same as the month and year of the last dose date of double-blind study medication, then the last day of the month will be assigned to the missing day.

#### **A.5 Missing Date Imputation for Last Dose Date**

Imputed last dose date = earliest date of (last drug dispense date + number of days of drug dispensed, date of death, date of EOT/EOS visit, and other dates as appropriate).

## APPENDIX 2. ANALYSIS VISIT WINDOWS

### A.2. Analysis Windows

Analysis visits are defined by the windows that will have the widths of the corresponding assessments centered at the scheduled time. Unscheduled visits within a visit window defined below will be grouped into the closest scheduled visits based on the visit date.

**Table 6: Analysis Visit Window for Vital Signs**

Analysis Visit	Target Day	Start Day	End Day
Baseline	Last value before the first study drug infusion (or randomization date if no infusion received)		
Day 1 post-dose	1	1	1
Week 2	15	2	22
Week 4	29	23	36
Week 6	43	37	50
Week 8	57	51	64
Week 10	71	65	78
Week 12	85	79	92
Week 14	99	93	106
Week 16	113	107	120
Week 18	127	121	134
Week 20	141	135	148
Week 22	155	149	162
Week 24	169	163	176
Week 26	183	177	190
Week 28	197	191	204
Week 30	211	205	218
Week 32	225	219	232
Week 34	239	233	246
Week 36	253	247	260
Week 38	267	261	274
Week 40	281	275	288
Week 42	295	289	302
Week 44	309	303	316
Week 46	323	317	330
Week 48	337	331	344
Week 50	351	345	358
Week 52	365	359	**

\*\* before the first study drug infusion in the OLE period or end of randomization treatment period

Note: The data on a study day with infusions will be used as a priority for summary tables whenever possible.

Note: All assessments beyond 60 days post last infusion will be excluded from summary tables or figures.

**Table 7: Analysis Visit Window for Physical Examination**

Analysis Visit	Target Day	Start Day	End Day
Baseline	Last value before the first study drug infusion (or randomization date if no infusion received)		
Week 12	85	2	120
Week 22	155	121	190
Week 32	225	191	260
Week 42	295	261	330
Week 52	365	331	**

\*\* before the first study drug infusion in the OLE period or end of randomization treatment period

Note: All assessments beyond 60 days post last infusion will be excluded from summary tables for labs.

**Table 8: Analysis Visit Window for Pulmonary Function Tests (PFT)**

Analysis Visit	Target Day	Start Day	End Day
Baseline	See Section 5.3.2		
Week 12	85	2	120
Week 22	155	121	190
Week 32	225	191	260
Week 42	295	261	330
Week 52	365	331	**

\*\* before the first study drug infusion in the OLE period or end of randomization treatment period

Note: All assessments beyond 60 days post last infusion will be excluded from summary tables for labs.

**Table 9: Analysis Visit Window for Muscle Function Tests (MFT)**

Analysis Visit	Target Day	Start Day	End Day
Baseline	Last value before the first study drug infusion (or randomization date if no infusion received)		
Week 16	113	2	155
Week 28	197	156	239
Week 40	281	240	323
Week 52	365	324	**

\*\* before the first study drug infusion in the OLE period or end of randomization treatment period

Note: All assessments beyond 60 days post last infusion will be excluded from summary tables for labs.

**Table 10: Analysis Visit Window for Laboratory Tests**

Analysis Visit	Target Day	Start Day	End Day
Baseline	Last value before the first study drug infusion (or randomization date if no infusion received)		
Week 8	57	2	85
Week 16	113	86	141
Week 24	169	142	197
Week 32	225	198	253
Week 40	281	254	309
Week 48	337	310	365
Week 56	393	366	**

\*\* before the first study drug infusion in the OLE period or end of randomization treatment period

Note: All assessments beyond 60 days post last infusion will be excluded from summary tables for labs.

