
The first three doses of the investigational product (IP) infusion will be administered at a healthcare facility/study site. Subsequent IP infusion(s) will be given in a healthcare facility or home healthcare may be provided as an option for interested subjects at study sites in geographic areas where such service could be feasibly provided.
 
An Independent blinded Centralized Imaging Charter will be formed to interpret the MRIs mentioned as endpoints in this study. Standardization is important for all clinically used MRI measures, and is essential for the study imaging endpoints, to reduce variability and to ensure interpretability of the results.

STUDY PERIODS

Screening period: Up to 4 weeks
 
Treatment period: 52 weeks (last dose on week 52)
 
Safety Follow-up period/End of Study (EOS): A visit 28 days (+/- 3 Days) and a final safety follow-up phone call 60 days (+ 3 Days) after the last dose
 
Efficacy Assessment Period (EAP): At Week 52
 
Open label Extension (Appendix 3): Continued treatment with pamrevlumab

SUBJECT ELIGIBILITY CRITERIA

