6.1.2. Randomized Treatment Period

The study procedures and assessments are presented for the Randomized Treatment phase in [Appendix 1](#) and [Appendix 3](#) for the OLE.

The Randomized Treatment Phase begins on Day 0 (first infusion of IP) and continues through Week 52. Visit windows are within ± 3 days of the scheduled visit date (14 days from prior visit). Visit dates should be scheduled based on the previous visit, not the baseline visit.

Subjects who complete 52 weeks of treatment may be eligible to rollover into the OLE study where all subjects will be treated with pamrevlumab. If a subject discontinues the main study early for any reason, they will not be eligible for inclusion in the OLE.

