- f.) Full physical exam including chest auscultation
- g.) SAEs are collected from date of consent through EOS. AEs are collected from Day 0 through EOS. Number and percentage of bone fractures is captured from Day 0 through EOS. Bone fractures should be collected in the EDC as AEs, naming them using the specific guidelines in the electronic case report form completion guidelines.
- See [Section 7](#) for follow-up of AEs.
- h.) Concomitant medications and nondrug therapies must be reported beginning after informed consent is obtained and ending 60 days after the last treatment. Refer to [Section 5.2.2](#) for additional information on prohibited concomitant medications
- i.) HAHA, HAHA-NA and PK samples. See [Appendix 2](#) for PK, HAHA, and HAHA-NA sampling time points.
- j.) MFTs: Performance of Upper Limb (v. 2.0), and Hand Grip Test.
- k.) Local labs may be drawn prior to MRIs at the discretion of the investigator.
- l.) Vital signs (pulse, respiration, sitting BP, temperature) to be collected at every visit: within 30 minutes pre-infusion, and within 30 minutes after completion of infusion.
- m.) MFTs and PFTs are collected at screening and must be repeated prior to randomization and first infusion on Day 0. They may be conducted up to 3 days in advance of the Day 0 visit. The PFT results from both time points will be used to establish baseline values. The results from MFTs at Day 0 will be used to establish baseline.
- n.) Genetic Analysis samples will be collected in PAXgene tube; samples will be collected only from subjects who consent for this test. If subject consents to this optional sample, it may also be collected at an Unscheduled timepoint if it is not collected initially at Day 0.
- o.) Duchenne Video Assessment to be performed remotely within the interval between the prior scheduled study visit and next scheduled study visit.

- p.) If the subject is not going into the OLE, he should complete a final safety follow-up that consists of a visit at week 56 and a final safety follow-up phone call 60 days (+3 days) after the last infusion visit.
- q.) PFTs, MFTs, DVA and MRI only to be done at the early termination visit
- r.) Randomization may be performed within 2 days prior to Day 0 visit, after subject is confirmed eligible (see footnote “m”).

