- The dosing period starts 14 days (± 3 days) after the parent study at the Week 52 visit. Subjects should be consented and eligibility confirmed during the Week 52 visit of the main study. Subjects will receive study drug every 2 weeks. The visit window for these visits is ± 3 days. Each visit should be scheduled based on the previous visit.
- Missed doses are not to be made up through extra visits. If a subject misses more than two infusions in an 8 week period, or two sequential infusions, the Sponsor Medical

Monitor should be notified. The reason for missed doses must be documented in the subject's clinical record.

- Vital signs (pulse, respiration, sitting BP, temperature) to be collected at every infusion visit: within 30 minutes pre-infusion, and within 30 minutes after completion of infusion. Vital signs to be collected one time during the safety follow-up.
- Physical exams should be performed in accordance with local standard of care (i.e., every 24 weeks). Any significant findings will be reviewed by the Investigator to determine appropriate reporting of adverse events.
- Muscle function tests and weight will be performed every 12 weeks. The Performance of the Upper Limb (PUL v. 2.0), will be performed to assess changes in upper extremity strength and the Performance of the Grip score will be performed to assess changes in hands strength. MFTs that cannot be performed or produce inadequate results according to test procedures during a specified visit should be performed by the next scheduled dosing visit. Video QC will not be required during the OLE.
- Weight will be performed every 12 weeks to make any weight based dose adjustments for the next 12 week period. Weight can be performed up to 2 weeks in advance of the 12 week interval visit.
- Pulmonary function tests (PFTs) will be performed using the same central vendor from the main study and completed every 24 weeks to assess changes in lung function: forced vital capacity (FVC), and peak expiratory flow rate (PEF; PEFr), and forced expiratory volume in 1 second (FEV1).

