### 5.3.3. Study Day Calculation

The day when a subject receives the first dose of study drug after randomization will be considered as Day 1 for all analysis.

Study day of an assessment/procedure is calculated as follows.

- For events on or after first dose:  
$$\text{Study day} = \text{Event date} - \text{Day 1 date} + 1.$$
- For events earlier than first dose:  
$$\text{Study day} = \text{Event date} - \text{Day 1 date}.$$

Note: Day 1 date will be the first dose date if the subject receives study treatment. Otherwise, it will be the randomization date if the subject does not receive the study treatment after randomization.

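### SAP Table 10 closes the Week 56 laboratory window before its own target day, so end-of-study labs of Week 52 finishers who skip the open-label extension miss the by-visit tables

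*SAP*

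**What the plan says.** The last two rows of SAP Table 10, read as visit, target day, start day and end day, are "Week 48 337 310 365" and "Week 56 393 366". The Week 56 row has no numeric end. Its footnote closes the window "before the first study drug infusion in the OLE period or end of randomization treatment period". A note under the same table drops from the laboratory summaries only what was measured more than 60 days after the last infusion, and SAP Section 5.3.1.1 applies the same 60-day limit to all safety assessments.

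The dates behind the footnote come from these places:

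- SAP Section 5.3.3 fixes the day count: "The day when a subject receives the first dose of study drug after randomization will be considered as Day 1 for all analysis".
- Protocol Section 6.1.2 states: "The Randomized Treatment Phase begins on Day 0 (first infusion of IP) and continues through Week 52". The protocol synopsis agrees: "Treatment period: 52 weeks (last dose on week 52".
- Protocol Section 6.1.3 puts the end-of-study (EOS) visit 28 days, plus or minus 3, after the last dose.
- Protocol Appendix 1, footnote p, says of a subject not going into the OLE that "he should complete a final safety follow-up that consists of a visit at week 56", followed by a telephone call.
- Protocol Appendix 3 starts OLE dosing 14 days, plus or minus 3, "after the parent study at the Week 52 visit", and defers the EOS visit of these subjects to the end of the OLE.

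SAP Section 5.5 assigns by-visit data by date windows and not by the visit label on the case report form. SAP Section 6.8.2 uses those analysis visits for the laboratory summaries and for one of its two CTCAE shift tables.

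**The concern.** A window should contain its target day, and this one does not. A programmer who follows the footnote literally gets a Week 56 row that cannot hold any scheduled Week 56 lab. Because Section 5.5 sets the nominal visit label aside, nothing else in the plan puts the value back.

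What is at stake is the only scheduled post-treatment laboratory panel of the main study for subjects who stop at about Week 52. Without it, their by-visit record ends with Week 48, whose target (Day 337) is 28 days before a last dose on Day 365 and 56 days before the EOS target on Day 393. No efficacy result is involved.

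**Working it through.** **Reproducing the table.** With the first dose as Day 1, week w falls on Day 7w + 1. Visits are 8 weeks (56 days) apart, so each window runs 28 days past its target and the next opens a day later.

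- Week 48: target 7 × 48 + 1 = 337; end 337 + 28 = 365.
- Week 56: target 7 × 56 + 1 = 393; start 365 + 1 = 366.

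These match Table 10, as do the rows for Weeks 8 to 40. The numeric entries are sound. Only the end rule of the last row is at issue.

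**Closing the Week 56 window by the footnote, on schedule.**

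| Subject | Footnote limit | Window | Scheduled EOS lab |
|---|---|---|---|
| Not entering the OLE | End of treatment: 7 × 52 + 1 = Day 365 | Day 366 to Day 365: empty | 365 + 28 ± 3 = Days 390 to 396: no window |
| Entering the OLE | First OLE infusion: 365 + 14 = Day 379 (376 to 382) | Day 366 to about Day 378 (375 to 381) | None in the main study |

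Neither window contains Day 393. For subjects entering the OLE nothing scheduled is lost, and the row could hold only stray unscheduled draws.

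**Does schedule drift rescue it?** Visits are timed from the previous visit, so the last dose may fall on some Day L other than 365. If the treatment period is taken to end on Day L, the window ends on Day L, and the EOS visit falls on Days L + 25 to L + 31, always later. Drift can open the window for a few days, but it cannot bring the EOS visit inside.

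**Which last-dose days are affected?** An EOS or early-termination lab is still caught if it falls by Day 365, the end of the Week 48 window.

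- L ≤ 334: the latest visit day is 334 + 31 = 365, so the lab always falls in the Week 48 window or an earlier one.
- L = 335 to 340: it depends on the exact visit day.
- L ≥ 341: the earliest visit day is 341 + 25 = 366, so the lab always misses.

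**After the change.** For a subject not entering the OLE with L = 365, a close at L + 60 gives Days 366 to 425. This contains Day 393 and the whole range 390 to 396.

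**The case against.** The strongest reply is that the SAP never defines the phrase used for the end of treatment, and that the intent is plain. A row targeted at Day 393 and a 60-day note under it make sense only if Week 56 labs are to be summarized. The same footnote stands under Tables 6 to 9, where the last row is Week 52 and it works, so it looks carried over. A careful programmer would probably notice.

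On intent this stands, and it makes the point a drafting error and not a chosen analysis. It does not make the text right. SAP Section 3.5 lists the 52-week treatment period separately from follow-up, and SAP Section 6.6.1.1.4 uses almost the same term for data up to Week 52. The wording therefore does not naturally stretch to cover follow-up.

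The second reply concerns harm. A reader might infer that post-treatment laboratory toxicity goes unsummarized in subjects who stop. The documents do not support that. SAP Section 6.8.2 also has a shift to the worst grade over the whole study, a summary and listing of Grade 3 or higher results, and an eDISH plot of maximum values, none tied to a visit window. Clinically significant abnormalities are reported as adverse events (Protocol Section 7.3.7), and treatment-emergent events are counted to 60 days after the last dose (SAP Section 6.8.1). All collected data are listed (SAP Section 5.1). This reply stands in full.

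**Conclusion.** The Table 10 end rule contradicts the row it belongs to and the 60-day note below it. If followed, it removes the Week 56/EOS labs of subjects who finish treatment at about Week 52 without entering the OLE from two outputs: the by-visit laboratory summaries and the by-visit CTCAE shift table. It is a minor point that should be corrected.

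Two wider inferences should be avoided. One is that all end-of-study and early-termination labs fall outside every window: labs after a last dose on Day 334 or earlier still land in a numbered window, and OLE entrants have no main-study EOS lab to lose. The other is a count of lost panels. SAP Section 7 mentions 97 dosed subjects, but those affected are subjects who finish at about Week 52 and do not continue, and neither document gives their number or an OLE uptake rate. Nor are the panels lost, since they remain in the outputs not tied to a visit.

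The conclusion assumes that treatment ends at the Week 52 dose, as both documents say, and that Week 56 is a laboratory visit, as Table 10 lists it.

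**What to change.** Replace the end rule of the Week 56 row in Table 10 with two explicit limits: the day before the first OLE infusion for subjects who enter the OLE, and 60 days after the last infusion for subjects who do not. For a last dose on Day 365 the second limit gives Days 366 to 425. Subjects entering the OLE keep the present limit in substance, so no open-label data enter the main-study tables. The footnotes to Tables 6 to 9 need no change for this point.

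The cost is one footnote and the matching line in the window derivation. It needs no new data and touches no efficacy analysis. The second limit only applies the 60-day rule that the SAP already states.
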